8.2.2. Exclusion criteria

Patient Participants

Currently enrolled in a clinical trial and/or using investigational product for the treatment of his or her hemophilia

8.3. Variables

Below is the current list of variables to be assessed in the in the study:

Physician Participants

Physician/Practice Characteristics

- Primary medical specialty;
- Board certification;
- Percentage of time spent in direct patient care;
- Percentage of their practice dedicated to the treatment of hemophilia;
- Number of moderate to severe hemophilia A and B patients currently managed;
- Number of hemophilia A and B patients currently participating in clinical trials;
- Insurance plans accepted.

Patient Treatment Pattern

- Current and previous hemophilia treatment;
- Reasons for discontinuation;
- Duration of treatment used;
- Whether prescription was prophylaxis or on-demand;
- Number of infusions per month prescribed;
- Frequency of doctor visits for management of hemophilia.

Patient Clinical Profile

- Height and Weight;
- Age of diagnosis;
- Primary symptoms;
- Disease severity;
- Joint health score;
- Comorbidities.

Patient Participants:

Patient Demographics

- Sex;
- Age;
- Race/ethnicity;
- Marital status;
- Household income;
- Education;*
- Employment status;*
- Health insurance type;
- Healthcare insurer;
- Pharmacy insurer.

*In the case of caregivers responding, caregiver's education and employment will also be collected.

Patient Clinical Profile

- Disease severity;
- Clotting factor level.

Patient Treatment

- When are infusions done;
- Number of infusions in a typical month;
- Previous and current hemophilia treatments;
- Duration of previous and current hemophilia treatments used;
- Recent Factor Use Behavior;
- Whether participated in clinical trials within the past 12 months.

Physician Patient Relationship

- Patient's relationship with his/her physician in regards treatment decisions for hemophilia rated as either paternalistic, informative, interpretive, or deliberate depending upon which relationship description the patient selects.

Validated Scales for Health-Related Quality of Life

- 36 Item Short Form Health Survey (SF-36 (adult)).³
- 10 Item Short Health Survey (SF-10 (caregiver reported for child)).⁴
- Hemophilia-Specific Quality of Life Index for Adults (HAEM-A-QOL (adult)).⁵
- Hemophilia-Specific Quality of Life Index (HAEMO-QOL (caregiver reported for child)).⁶

Health Insurance Claims Data from Patients

- Total services and healthcare costs (healthcare visits, factor).
- Hemophilia-specific services and costs (healthcare visits, factor).

8.4. Data sources

This study will be conducted with physicians and patients in an online setting. Prior to participating, patients will be asked to provide their informed consent in order to proceed with the web surveys and provision of their health care insurance claims.

The physicians participating in this research will be asked to reference their patient medical records for each enrolled patient during their portion of the study.

There will be three sources of data for each patient (or caregivers of patients in the case of minor patients):

- Patient responses to a web survey/questionnaire
- Physician responses to a CRF concerning the same patient
- Patients' medical and pharmacy claims data obtained directly by the patient from their healthcare insurer and provided to Kantar Health via a secure, dedicated email address.

No personal identifiable information will be captured in either the CRF or patient questionnaire. However, the medical claims component of the patient data may include confidential information. Therefore, we will ensure that all personal identifiable data are removed from the claims when the claims are received by Kantar Health. Once Kantar Health study staff receives claims via the dedicated email address, all identifying information (name, date of birth, or other individual identifiers) are redacted using mark-up application that puts a black bar over this data. The claims document is then numbered with the patient's anonymous study ID number and saved using the study ID number as the document name. The document is also password protected so that the redacting masks cannot be removed by other individuals. All patient data will be reported in aggregate form and participants will only be identified by a random unique ID for reference. Kantar Health will not link any study data to personal information of any patient or physician participant.

It is anticipated that claims data received will vary in type and degree of insurance data across different insurers. As such, the planned process is to extract some of the common variables as seen within sample claims such as date of service, carrier, provider type, service description, cost, and any procedural or diagnosis codes if present. The data will be entered and validated by Kantar Health. Final variable list and data format will be discussed with Pfizer prior to data entry.

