6. RATIONALE AND BACKGROUND

Hemophilia A and B are chronic inherited bleedings disorders caused by an X-chromosome linked deficiency in coagulation factors.¹ Although the incidence of hemophilia is relatively low, it imposes a high level of burden to sufferers, caregivers, and society. As hemophilia requires lifetime treatment it is associated with substantial costs, particularly direct costs. Factor replacement therapy, used for both prophylaxis and on-demand therapy, is the mainstay of hemophilia treatment and has been estimated to cost more than \$250,000 per adult in the United States. Depending on the disease severity and treatment regimen, factor replacement products accounts for 45% to 93% of the total medical costs for hemophilia.²

Newer, extended half-life treatments for hemophilia have recently been approved by the FDA). Alprolix is an extended half-life treatment that was approved by the FDA in March, 2014 for hemophilia B. And similarly, for hemophilia A, Eloctate was approved in 2014 and Adynovate in 2015. These newer, extended half-life drugs require less frequent administrations than Pfizer's BeneFIX (for hemophilia B) and Xyntha (for hemophilia A). Even a relatively small change in frequency of administration has the potential to translate into 50 or fewer infusions per year and a correspondingly smaller number of units infused per patient. The expected advantages of fewer infusions from extended half-life products include greater patient compliance, less disruptions in daily activities and less reliance on others to help with infusions.¹ However; these benefits are only realized if there is indeed fewer infusions associated with the extended half-life products compared with the standard half-life products. To date, little is known about real world administration patterns for extended half-life treatments in comparison to standard half-life treatments. Pfizer is seeking to understand whether Alprolix, Eloctate, and Adynovate are being dosed more often than their labeling indicates, thus potentially costing payors and patients more money compared to traditional treatments, like BeneFIX and Xyntha.

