8.9. Limitations of the research methods

Subject responses may be influenced by recall and self-presentation biases which could introduce additional error. Therefore the design of the study was approached with the intent to maximize the external validity of the findings by requesting patient's medical claims (as opposed to asking them to self-report their healthcare resource utilization for the past 12 months, which will require recall and estimation) and obtaining real-world medical records data via the CRFs from physician report.

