##### *Patient Treatment Pattern (from patient chart)*

- Current and previous hemophilia treatment
- Reasons for discontinuation
- Duration of treatment used
- Whether prescription was prophylaxis or on-demand
- Number of infusions per month prescribed

Protocol # B1821056  
Statistical Analysis Plan

- Frequency of doctor visits for management of hemophilia

*Patient Demographics (from patient chart)*

- Age
- Sex
- Race
- Weight
- Height
- Health insurance type

*Patient Clinical Profile (from patient chart)*

- Age of diagnosis
- Primary symptoms
- Disease severity
- Joint health score
- Comorbidities

Patient Participants (self-reported or caregiver reported):

*Patient Demographics*

- Sex
- Age
- Race/ethnicity
- Marital status
- Household income
- Education\*
- Employment status\*
- Health insurance type

Protocol # B1821056  
Statistical Analysis Plan

- Healthcare insurer
- Pharmacy insurer

\*In the case of caregivers responding, caregiver's education and employment will also be collected.

*Patient Clinical Profile*

- Disease severity
- Clotting factor level

*Patient Treatment*

- When are infusions done
- Number of infusions in a typical month
- Previous and current hemophilia treatments
- Duration of previous and current hemophilia treatments used
- Recent factor use behavior
- Whether participated in clinical trials within the past 12 months

*Physician Patient Relationship*

- Patient's relationship with his/her physician in regards treatment decisions for hemophilia rated as either paternalistic, informative, interpretive, or deliberate depending upon which relationship description the patient selects.

*Validated Scales for Health-Related Quality of Life*

*Global health-related quality of life scales*

36 Item Short Form Health Survey (SF-36; adult): The SF-36v2 is a multipurpose, generic health status instrument comprised of 36 questions. These items map onto eight health domains: physical functioning, physical role limitations, bodily pain, general health, vitality, social functioning, emotional role limitations, and mental health. In addition to these eight health domains, there are two component summary scores: the physical component summary (PCS) and the mental component summary (MCS).

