**Table 2. Example bivariate Table: Patient demographics among hemophilia A patients by standard half-life vs. extended half-life treatment. Note: a similar table would be created for hemophilia B patients.**

		Treatment Group							
		Standard Half-Life		Extended Half-Life		Total			
		% / Mean	N/ SD	% / Mean	N/ SD	% / Mean	N/ SD		
	Student								
Geographic Region	South								
	Northeast								
	Midwest								
	West								
Insurance	Coverage through employer								
	Coverage through spouse's/partner's employer								
	Coverage through parent's or legal guardian's employer								
	Individual/Family Plan- State Health Exchange								
	Individual/Family Plan- Self-purchased								
	Medicaid (MediCal for California)								
	Medicare								
	Veterans Administration (VA)/CHAMPUS								
	TRICARE								
	Not sure								
Healthcare insurer	Aetna								
	Anthem (Blue Cross and Blue Shield, Empire Blue Cross, Amerigroup, UniCare, CareMore, Wellpoint)								
	Centene								
	Cigna								
	Health Net								
	Human								
	Kaiser Permanente								
	Magellan Health								

Protocol # B1821056  
 Statistical Analysis Plan

**Table 2. Example bivariate Table: Patient demographics among hemophilia A patients by standard half-life vs. extended half-life treatment. Note: a similar table would be created for hemophilia B patients.**

	Treatment Group							
	Standard Half-Life		Extended Half-Life		Total			
	% / Mean	N/ SD	% / Mean	N/ SD	% / Mean	N/ SD		
Molina Healthcare								
UnitedHealth Group								
WellCare Health Plans								
Other, specify								
Different insurer covering prescription or pharmacy benefits?	Yes, different insurer for prescriptions							
	No, same insurer as medical							
	Don't know							
On patient assistance program for hemophilia medication?	Yes							
	No							
	Don't know							

**Table 3. Example bivariate table: Patient health characteristics, disease characteristics, and treatment history among hemophilia A patients by standard half-life vs. extended half-life treatment (from patient chart). Note: a similar table would be created for hemophilia B patients.**

	Treatment Group							
	Standard Half-Life		Extended Half-Life		Total			
	% / Mean	N/ SD	% / Mean	N/ SD	% / Mean	N/ SD		
BMI category	BMI: underweight							
	BMI: normal weight							
	BMI: overweight							
	BMI: obese							
	Declined to answer							

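### Claims come from the healthcare insurer alone and are not checked for completeness, so some submitters' factor cost may enter the cost models understated

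*Protocol*

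**What the plan says.** Protocol 8.4 gives the third data source as "medical and pharmacy claims data obtained directly by the patient from their healthcare insurer". It expects submissions to differ between insurers and responds by extracting the variables they have in common.

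Elsewhere the plan expects more than one payer or supply route:

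- Protocol 8.3 lists healthcare insurer and pharmacy insurer as separate items. SAP Table 2 has the row "Different insurer covering prescription or pharmacy benefits" with the level "Yes, different insurer for prescriptions".
- SAP Table 2 also has the row "On patient assistance program for hemophilia medication". The type of assistance is not stated.
- The only patient exclusion is "Currently enrolled in a clinical trial and/or using investigational product for the treatment of his or her hemophilia". The questionnaire separately records "Whether participated in clinical trials within the past 12 months" (SAP 4.1), so earlier participants are eligible.

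SAP 6.2.3 models total and hemophilia-specific healthcare and Rx costs by treatment group. SAP 5 sets missing-value rules for CRF and questionnaire items only. SAP 6.2.2 recognises patients who do not provide claims, but says nothing of those who provide incomplete ones. The cost allocation algorithm (SAP 4.1) and the final claims variable list (Protocol 8.4) are deferred. The claims window is not defined in Protocol 8.4 or the SAP. Protocol 8.9 only implies one, by contrasting claims with self-report: "as opposed to asking them to self-report their healthcare resource utilization for the past 12 months".

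**The concern.** Read literally, Protocol 8.4 lets a patient send a genuine file that shows visits but little or no factor, because another payer or another supply route covered the factor. Nothing in the plan would detect this. The double data entry in Protocol 8.8 checks transcription and cannot show that a payer's file is missing. A negative binomial model (SAP 6.2.3) accepts zero or very small values, so such a record would pass through unnoticed.

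Every eligible patient must infuse at least three times a month and have been on the current product for at least six months. Absent factor claims are therefore much more likely to reflect incomplete capture or another supply route than no use of factor.

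At stake are the cost comparisons in SAP Tables 7 and 8. The SAP Introduction makes potential extra cost to payors and patients part of the study's rationale. Protocol 8.9 presents claims as the safeguard against recall error, which holds only if the claims are complete.

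**Working it through.** **1. The plan's own figure.** Protocol 8.5 gives d = 0.46 for 75 vs 75, two-sided 0.05, 80% power. Check: (1.960 + 0.842) × √(2/75) = 0.457, or 0.460 with the t distribution. It reproduces, so the sample-size statement is not in question.

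**2. Loss for one submitter.** Protocol 6 states that "factor replacement products accounts for 45% to 93% of the total medical costs for hemophilia". With factor share s and no factor claims, recorded cost is 1 − s of the true value: 1 − 0.45 = 0.55, and 1 − 0.93 = 0.07. Factor cost itself is recorded as 0. For a past trial participant the loss may be partial. If the window is 12 months and trial-supplied factor filled six of them (both assumed, with even cost over time), the understatement is 0.5 × 0.45 = 22.5% to 0.5 × 0.93 = 46.5%.

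**3. Effect on the comparison of arms.** Let a fraction f of submitters lose all factor claims, with equal true costs in both arms. The recorded mean is 1 − f·s of the true mean. The documents give no value of f for either arm, so the splits below are assumptions.

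| f, arm 1 vs arm 2 | s = 0.45 | s = 0.93 | factor cost only (s = 1) |
|---|---|---|---|
| 20% vs 10% | 0.910/0.955 = 0.953 | 0.814/0.907 = 0.897 | 0.8/0.9 = 0.889 |
| 30% vs 10% | 0.865/0.955 = 0.906 | 0.721/0.907 = 0.795 | 0.7/0.9 = 0.778 |

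Total cost therefore looks 4.7% to 10.3% lower in the first case and 9.4% to 20.5% lower in the second. Factor cost looks 11% and 22% lower.

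**4. Chance of a false difference.** Take mean factor cost μ = $250,000 (the plan's figure is more than this per adult, with no period stated), 75 submitters per arm, SD/mean of 0.3, 0.5 or 0.8 (assumed), and a simple z-test in place of the planned model. With a share q recorded as zero, the mean is μ(1 − q) and the variance is (1 − q)SD² + q(1 − q)μ².

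For 10% vs 0% at SD/mean 0.5:
- Difference: $25,000.
- Variances: 1.5625 × 10¹⁰ and 1.96875 × 10¹⁰.
- Standard error: √(3.53125 × 10¹⁰/75) = $21,699, so z = 1.152.
- Rejection probability: 1 − Φ(1.960 − 1.152) + Φ(−1.960 − 1.152) = 21%.

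At SD/mean 0.3 and 0.8 the rejection probability is 40% and 12%. For 20% vs 0% (difference $50,000) it is 86%, 60% and 33% at SD/mean 0.3, 0.5 and 0.8.

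**5. Equal loss in both arms.** With 10% in each arm and equal true means there is no false difference, but zeros inflate the variance. For a true d of 0.46, power falls from 80% to 42.5%, 58.7% and 67.6% at SD/mean 0.3, 0.5 and 0.8.

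**6. What covariate selection can do.** SAP 6.2.2 screens Table 2 variables by arm as candidate covariates, so the insurer and assistance rows can enter the cost models. Assume selection at p < 0.05 with 75 per arm; power of the comparison is Φ[(Δ − 1.960·SE₀)/SE₁].

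- 30% vs 10%: SE₀ = √(2 × 0.20 × 0.80/75) = 0.0653, SE₁ = √((0.21 + 0.09)/75) = 0.0632, giving Φ(1.14) = 87%.
- 20% vs 10%: SE₀ = 0.0583, SE₁ = 0.0577, giving Φ(−0.25) = 40%.

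A large imbalance would usually be picked up; a moderate one would be missed more often than not. If the flag is selected and marks the loss exactly, a log-link model largely removes the bias in the ratio. One simulation (69% of cost lost in flagged patients, 30% vs 10%, assumed cost distribution) moved the ratio from 0.86 to 1.01. The adjusted means in Table 8 would still contain the unrecorded cost as if it were not there.

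**The case against.** The strongest case on the other side is that this is a loose phrase, not a defect. Protocol 8.4 does ask for pharmacy claims, and healthcare insurer may be meant generically. The documents do not say whether factor is billed under the medical or the pharmacy benefit. Assistance may be copay help, in which case the insurer's claim still exists. That a past trial supplied the factor is an inference. No passage says absent factor is coded as zero, and the allocation algorithm, Data Management Plan and patient-facing materials may deal with it. The insurer and assistance flags are candidate covariates, not only descriptive rows. The primary objective names dosing and resource utilization rather than cost, and infusion counts come from the chart and questionnaire, so they are untouched.

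Most of this stands, and it limits the point. A reader might infer that factor is certainly absent from these patients' claims, that their recorded factor cost is near zero, or that the comparison is biased in a known direction. The documents support none of these: they show that loss is possible and unchecked, and they give no frequencies by arm.

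The objection does not supply a completeness rule. The deferred algorithm is described as defining cost groupings, not as testing whether a file is complete. Covariate selection depends on the observed imbalance, and adjustment cannot restore cost that was never recorded.

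**Conclusion.** The point holds as a gap in data capture and analysis rules. The plan anticipates patients whose factor may be paid for or supplied outside the one payer it names, and it has no rule for incomplete submissions. An affected submitter's hemophilia cost can be understated by up to the factor share, 45% to 93%, and by less where only part of the factor is missing.

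The effect on the comparison of arms depends on frequencies that the documents do not give. The percentages, dollar differences and rejection rates above rest on assumed splits, complete factor loss in affected patients, assumed cost variability and no adjustment. They show that modest unequal loss would matter and that equal loss would cost power; they do not predict a result. The dosing comparison based on infusion counts is not affected. The change should be made before the cost analyses are run.

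**What to change.** - **Protocol 8.4:** request claims from every insurer the patient names, medical and, if different, pharmacy, and state the claims window.
- **SAP 4.1 and 6.2.3:** define a factor-cost-evaluable set as submitters with files from all named payers, and with factor claims present and plausible against the CRF or reported infusions over that window. Run the cost models in this set.
- **SAP 5:** treat absent factor claims as missing, not zero. Keep the other submitters in visit counts where their medical claims are complete.
- **Assistance-programme and past-trial patients:** do not exclude them automatically, because their claims may be complete. Leave them out of the factor-cost models only where factor claims are absent or incomplete, and add a sensitivity analysis that includes or omits these patients.
- **Reporting:** give the numbers excluded by arm and by reason.

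The cost is one instruction to patients, a completeness check at data entry and some SAP wording. Insurer names, assistance use and trial participation are already collected; assistance type and whether a trial supplied factor are not listed, which is another reason to base the rule on the claims themselves. The downside is fewer patients in the cost models and possible selection if exclusions differ by arm, which the counts by arm and the sensitivity analysis would help to show.

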8.5. Study size

The study will involve approximately 300 patients recruited from approximately 30 participating sites.

This study will compare Xyntha vs. Eloctate /Adynovate among hemophilia A patients and Alprolix vs. BeneFIX among hemophilia B patients. For a mean difference comparing two independent means with the anticipated sample sizes (75 vs. 75; 150 total) with $\alpha=0.05$, two-sided, 80% power, the expected minimal detectable effect (MDE) would be Cohen's $d=0.46$. This study with the anticipated sample size is powered to detect at least a moderate effect size.

8.6. Data management

Study data will come from three sources: (1) the patient-reported outcomes and treatment patterns collected in the form of an online survey, (2) the CRF by physicians collected in the form of an online survey, and (3) the data extracted from patient medical and pharmacy claims which will be received as paper files or pdf downloads.

Both patient and physician participants will be entering their survey responses via survey links that are unique to each participant so that each participant is identified by a random unique identification (ID) number. The database which houses the survey responses allows for direct exportation into statistical software (e.g., Statistical Package for the Social Sciences (SPSS), Statistical Analysis System (SAS), Stata). Because each participant will be identified by a random unique ID number, the working data files will not contain any identifying information apart from the ID number. No identifying information (e.g. names, addresses, or other distinguishing information) will be collected in the surveys will not be designed with such variables in mind.

Regarding the claims data, a dedicated email address for receiving this data will be set up to receive this data directly from the patients (?) for this particular study to be accessed only by a select group of the research team at Kantar Health. Any personal identifiable data available in the claims, such as names, dates of birth, social security numbers, etc., will be omitted during data entry (performed through an external coding vendor) and all participants will only be identified by an assigned random unique ID for reference. Furthermore, the original claims data will be saved for 24 months after study completion and then backed up / destroyed according to Pfizer requirements. The file containing claims data will be created in an agreed upon format between Pfizer and the Kantar Health. Data files provided to the broader Kantar Health research team or Sponsor will not include any personal identifying information as this information is either not collected or have been omitted/redacted as indicated above to preserve confidentiality. Details of data entry management are contained in the Data Management Plan.

